2.4.2 Secondary Endpoint

(1) Immediate intraoperative success rate [Intraoperative]

Definitions of Immediate Technical Success: The delivery system is successfully delivered to the intended location, the thoracoabdominal aortic stent graft system is successfully deployed, the branch vessels are successfully reconstructed, and the delivery system can safely withdraw from the body; No type I or III endoleaks requiring intervention; No conversion surgery.

(2) Perioperative delivery-related complication rate [intraoperative and pre-discharge]

Delivery-related complications refer to intraoperative conveyor-related conversion to laparotomy, bleeding, hematoma, and pseudoaneurysm in the delivery approach

(3) Aneurysm-related mortality rate [6, 12 months postoperation]

Aneurysm-related death is defined as death caused by a ruptured aneurysm or by surgery to treat thoracic and abdominal aortic aneurysm, pararenal abdominal aortic aneurysm.

(4) Incidence rate of Serious Adverse Events (SAEs) [6, 12 months postoperation]

Serious adverse events refers to death or serious deterioration of patient health condition during the clinical trial, including fatal illness or injury, permanent impairment of body structure or function, hospitalization or prolonged hospital stay, and medical or surgical intervention to avoid permanent impairment of body structure or function; Events that cause to fetal distress, fetal death, or congenital abnormalities, congenital defects, etc.

(5) Incidence rate of device-related adverse events [6, 12 months postoperation]

Adverse events refers to adverse medical events that occur during clinical trial, whether or not related to the investigational medical device. However,postoperative stress responses, such as fever,constipation, etc., should be distinguished by the investigator judgment as normal postoperative stress responses and therefore do not need to be recorded as adverse events. Device-related adverse events refers to those that are judged by the investigator to be positively related, possibly related, or undeterminable to the investigational medical device.

(6) Incidence rate of Type I or Type III endoleaks [6 and 12 months postoperation]

Type I endoleaks, also known as peri-graft endoleaks or graft-related endoleaks, refers to endoleaks formed by the inability of tight-fitting between the stent blood vessels and autologous blood vessels, resulting in continuous blood flowinto the aneurysm lumen, including proximal Type I endoleaks and distal Type I endoleaks. Type III endoleaks refers to the continuous flow of blood into the aneurysm cavity caused by the inability of the stent blood vessel to seal its own interface or the rupture of the artificial vessel.

(7) Incidence rate of Thoracic Abdominal Aortic Stent Graft System Displacement [6, 12 months postoperation]

Stent migration requiring intervention.

(8) Incidence rate of branch stent occlusion [6, 12 months postoperation]

The main stent and branch stent were structurally intact, the blood flow in branch stent was unobstructed, and there was no branch stent occlusion caused by thrombus.

(9) Incidence rate of conversion of thoracic and abdominal aortic aneurysms to open surgery or secondary interventional surgery [6, 12 months postoperation]

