2.3 Inclusion and Exclusion Criteria

2.3.1 Inclusion criteria

- (1) Age ≥ 18 and ≤ 80 years;
- (2) Patients diagnosed with type Crawford I-V thoracoabdominal aortic aneurysmsa and pararenal abdominal aortic aneurysm, and should meet at least one of the following conditions:
 - a) The maximum diameter of thoracoabdominal aortic aneurysms and

pararenal abdorminal aortic aneurysm > 50 mm;

- b) Rapid growth of sac >5 mm in diameter in the most recent 6 months;
- c) Definite symptoms of abdominal pain and low back pain associated with thoracicabdominal aortic aneurysms.
- (3) Patients with four indispensable reno-visceral arteries including superior mesenteric artery, celiac trunk and bilaterial renal arteries.
- (4) Proximal landing zone 20 36 mm in diameter;
- (5) Proximal landing zone ≥ 25 mm in length;
- (6) If distal landing zone in abdominal aorta, distal landing zone should be 12-36mm in diameter and ≥15 mm in length.
- (7) The visceral vascular branches landing zone 6~13 mm in diameter and ≥15 mm in length;
- (8) The renal artery landing zone 4.5~9 mm in diameter and ≥ 15 mm in length;
- (9) Patients who using the abdominal aortic bifurcation stent graft system should also meet the following criteria:
 - a. The iliac artery landing zone 7 ~25 mm in diameter;
 - b. The iliac artery landing zone ≥ 15 mm in length;
- (10) Patients with appropriate iliacofemoral access and at least one patent upper extremity access;
- (11) Patients who can understand the purpose of the trial, volunntarily participate and sign the informed consent form, and are willing to complete the follow-up according to the requirements of the protocol;

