3.1 Sample size calculation

This study is a feasibility study and the total sample size expected to be 15.

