3.2.4 Secondary endpoint analysis

Immediate intraoperative success rate, incidence rate of perioperative delivery-related complications, aneurysm-related mortality rate, incidence rate of device-related AEs, SAEs, incidence rate of type I or III endoleaks, incidence rate of stent migration, incidence rate of branch stent occlusion, and incidence rate of open or secondary interventional procedures were calculated, and trial discontinued due to adverse events and cases of SAEs were specifically noted.

4. Ethical issues and informed consent of clinical trial

Prior to the clinical trial, the investigator needs to submit the study protocol, informed consent form and other relevant documents to the Medical Ethics Committee. Clinical trials may not be started until Ethics Committee approval has been obtained. Any changes to the protocol must be approved by the Ethics Committee before they can be implemented.

Before each subject is enrolled in this study, it is the responsibility of the investigator to provide a complete and comprehensive description of the informed consent form in writing to the subject or the subject's guardian. The investigator should give sufficient time for the subjects to understand the details of the study before signing. The informed consent form was signed by the investigator and the subject or the subject's legal representative. The informed consent form is made in duplicate, and each party keeps one copy.

Subjects participating in this study will have free access to the Thoracic and Abdominal Aortic Stent Graft System and study-related examinations during postoperative follow-up, as well as medical guidance from physicians and device-related insurance coverage during follow-up.

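### The list defining delivery-related complications omits non-bleeding access injury, so that secondary rate may be understated

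*Combined protocol and SAP*

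**What the plan says.** Section 2.4.2, endpoint (2), is a secondary endpoint assessed during the operation and up to discharge. Its definition begins "Delivery-related complications refer to intraoperative conveyor-related conversion to laparotomy" and continues with "bleeding, hematoma, and pseudoaneurysm in the delivery approach". That makes four items: one conversion event and three bleeding-type events at the access route.

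Inclusion criterion (10) in section 2.3.1 shows which vessels are at risk: "Patients with appropriate iliacofemoral access and at least one patent upper extremity access".

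Section 3.1 fixes the size of the study: "This study is a feasibility study and the total sample size expected to be 15". Section 3.2.4 says only that the rate will be calculated, in a list that runs "Immediate intraoperative success rate, incidence rate of perioperative delivery-related complications, aneurysm-related mortality rate" and onward. It gives no threshold, test or interval.

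Two other secondary endpoints in section 2.4.2, both reported at 6 and 12 months, bear on the point. Serious adverse events include those needing "medical or surgical intervention to avoid permanent impairment of body structure or function". Device-related adverse events are those that the investigator judges "positively related, possibly related, or undeterminable to the investigational medical device".

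**The concern.** The endpoint's name promises the harm done by delivering the device, but its list covers only conversion and bleeding. Access through iliofemoral and upper-limb arteries can also injure a vessel without bleeding: by dissection, by thrombosis or occlusion, or by embolism with limb ischaemia. Under the definition as written, a patient whose only access event is of that kind is scored as having no delivery-related complication.

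This is the one endpoint devoted to complications of delivery, in a study whose stated purpose is feasibility. Because the analysis section only calculates the rate, the meaning of the figure rests wholly on the definition. A reader who sees a low rate would take it to cover access injury in general, when it covers only part of it.

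**Working it through.** **No plan figure to reproduce.** The documents state no expected delivery complication rate, and the sample size of 15 comes without inputs. The check is therefore a reading of the definition, followed by arithmetic for scale.

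**Step 1: is the list closed?** The definition in endpoint (2) uses a plain verb of definition and then four items, with no open-ending phrase. Elsewhere the protocol marks open lists expressly: the reasons for discontinuation in section 2.3.3 are stated to be non-exhaustive, and the serious adverse event definition in section 2.4.2 uses open-ended wording. Set against these, endpoint (2) reads as closed.

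**Step 2: which access events does it miss?**

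| Access event caused by the delivery system | Counted under endpoint (2)? |
|---|---|
| Bleeding, haematoma, pseudoaneurysm | Yes, named |
| Conversion to laparotomy | Yes, named |
| Rupture of an access artery | Not named, but would normally appear as one of the four items |
| Dissection | Only if a listed event also occurs |
| Thrombosis or occlusion | Only if a listed event also occurs |
| Distal embolism or limb ischaemia | Only if a listed event also occurs |

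Open repair of a femoral or brachial artery is not a laparotomy, so the conversion item does not bring these events in.

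**Step 3: does another endpoint fill the gap?**

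- The major adverse event list in section 2.4.1 has no access-vessel or limb event.
- Immediate technical success, endpoint (1), requires safe withdrawal of the delivery system. The term safe is not defined, and the endpoint is intraoperative only, so an occlusion found later but before discharge falls outside it.
- Serious adverse events and device-related adverse events can capture the omitted events. They pool them with unrelated events, are reported at 6 and 12 months, and do not feed the delivery rate.
- The visit table in section 2.5.2 lists a chest and abdomen examination but has no row for a limb or pulse examination. Capture of milder limb events relies on general adverse event reporting.

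**Step 4: what is one missed patient worth?** The input is N = 15 (section 3.1). The shift per patient is 1/15 = 6.7 percentage points. Exact (Clopper-Pearson) 95% intervals show how the reported result would change:

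| Patients counted | Rate | Exact 95% interval |
|---|---|---|
| 0/15 | 0.0% | 0 to 21.8% |
| 1/15 | 6.7% | 0.2 to 31.9% |
| 2/15 | 13.3% | 1.7 to 40.5% |

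**Step 5: how likely is such an event?** The documents give no frequency, so the per-patient risk p below is purely an assumption. The chance of at least one omitted-type event among 15 patients is 1 − (1 − p)^15:

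| Assumed p | Chance of at least one in 15 |
|---|---|
| 1% | 14.0% |
| 2% | 26.1% |
| 5% | 53.7% |
| 10% | 79.4% |
| 15% | 91.3% |

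If p is taken as the risk of any event of these types, the results are upper figures for the chance of a missed patient, because a patient who also has a listed event is counted anyway. The spread from 14% to 91% shows that the answer is set by the assumption, so no single value should be quoted as the expected shortfall.

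**The case against.** The case for leaving the definition alone has several parts.

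- **The safety data are not lost.** A serious occlusion or limb ischaemia would meet the serious adverse event definition, and the attribution rule for device-related events is wide. Both rates are to be calculated under section 3.2.4. This stands: for such an event the question is which rate shows it. It does not answer the point that the rate named for delivery complications would not show it.
- **Deliverability is measured elsewhere.** Endpoint (1) covers reaching the target, deployment and withdrawal. This stands in part. Endpoint (1) measures whether delivery succeeded. It is not a count of access injury and does not extend to discharge.
- **Nothing inferential depends on it.** This is a descriptive secondary rate in a single-group feasibility study with no threshold. That stands, and it keeps the point small.
- **The English reads as a translation.** An open-ended term may have been lost. This stands as a caution, and the source-language text should be checked.

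A reader might also infer that the rate is certainly understated, or that access-artery rupture goes uncounted. The documents support neither. The rate falls only if an omitted event occurs in a patient with no listed event, and nothing in the documents says how often that happens. Rupture would normally enter as bleeding, haematoma, pseudoaneurysm or conversion.

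**Conclusion.** The point holds in a limited form. As written, endpoint (2) does not count dissection, thrombosis or occlusion, distal embolism or limb ischaemia caused by the delivery system unless a listed event accompanies it. The delivery-related complication rate may therefore be too low, and it cannot be too high for this reason. Each affected patient is 6.7 percentage points. The expected size cannot be derived.

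The conclusion rests on two assumptions: that the list is closed in the source language as it is in English, and that at least one such event occurs in a patient without a listed one. The primary endpoint, the sample size and the other secondary rates do not change. This is a cheap improvement to a descriptive endpoint and not a flaw in the design.

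**What to change.** In section 2.4.2, define endpoint (2) as any access-vessel injury or limb ischaemia attributable to the delivery system, from the procedure to discharge: bleeding, haematoma, pseudoaneurysm, dissection, thrombosis or occlusion, and distal embolism, together with conversion to laparotomy. Classify events from the adverse event records that the trial already collects. Report the rate under the present four-item list beside the wider one, so that both can be read.

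The cost is one sentence in section 2.4.2, a matching line in section 3.2.4 for the second rate, and ethics committee approval of the change, which section 4 requires for any protocol change. No new visit or test is needed, though classification will be only as complete as the adverse event reporting of limb events. The downside is a possibly slightly less favourable rate.

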2.2. Method Selection and Reasons

There are no commercially available stent-graft systems for the effective endovascular treatment for thoracoabdominal aortic aneurysms and pararenal abdominal aortic aneurysm in China, so a prospective, single-group feasibility study is proposed for this study.

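### Investigators may leave an open-ended class of post-operative events unrecorded before relatedness or seriousness is assessed, so the device-related AE rate can be under-counted but not over-counted

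*Combined protocol and SAP*

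**What the plan says.** The affected endpoint is "5) Incidence rate of device-related adverse events [6, 12 months postoperation" months, in section 2.4.2 of the combined protocol and SAP. Its definition has three steps, in this order:

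1. A broad definition of an adverse event: "Adverse events refers to adverse medical events that occur during clinical trial, whether or not related to the investigational medical device".
2. An exemption for "postoperative stress responses, such as fever,constipation, etc", which "should be distinguished by the investigator judgment as normal postoperative stress responses and therefore do not need to be recorded as adverse events".
3. A relatedness rule, under which device-related events are those "judged by the investigator to be positively related, possibly related, or undeterminable to the investigational medical device".

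Endpoint (4) in the same section defines serious adverse events. The definition includes "hospitalization or prolonged hospital stay, and medical or surgical intervention to avoid permanent impairment of body structure or function".

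Section 2.2 states the design: "a prospective, single-group feasibility study is proposed for this study". Section 3.1 gives the size: "This study is a feasibility study and the total sample size expected to be 15". Section 3.2.4 says only that the secondary rates will be calculated. It describes no interval, test or sensitivity analysis for them.

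**The concern.** Step 3 is cautious: where the relation to the device cannot be settled, the event counts against the device. Step 2 acts earlier and allows the same doubt to be settled the other way, because an event accepted as an ordinary reaction to surgery never becomes an AE and so never reaches step 3.

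The exemption has no limits in the text. There is no closed list, no criterion for severity, onset or duration, no time window, no log of what was exempted and no second look. It also does not say that seriousness is checked before an event is set aside.

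At stake is the credibility of a safety count. The study has one group, so no control arm passes through the same filter, and with no hypothesis test planned the descriptive safety counts are a main product. Fever is also a sign one would want to see recorded here: exclusion criterion (16) shows that the protocol itself treats graft infection as a risk.

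**Working it through.** The plan gives no expected device-related AE rate, no rate of post-operative fever or constipation, and no formula behind the sample size. There is no planned figure to reproduce. The check is therefore a reading of the text followed by a sizing.

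**Reading.** Take an event of doubtful cause, for example a fever some days after implantation.
- If the investigator accepts it as an ordinary reaction to surgery, step 2 applies. It is not recorded as an AE and adds 0 to the numerator.
- If the investigator considers that its relation to the device cannot be determined, step 3 applies. It adds 1 to the numerator, if that patient has no other qualifying event.

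Nothing in section 2.4.2 says which question is asked first when both answers are tenable. The same holds for seriousness: a fever that prolongs the hospital stay meets the definition in endpoint (4), but the text does not say that this overrides the exemption.

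**Direction.** The exemption only removes events. A wrong use of it can lower the count or leave it unchanged, never raise it.

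**Size per patient.** The denominator is 15 (section 3.1), assuming all 15 are analysed. One missed patient costs 1/15 = 6.7 percentage points.

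**What that does to the reported rate.** Rates are x/15 with exact (Clopper-Pearson) 95% limits:

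| Patients with a device-related AE | Rate | 95% limits |
|---|---|---|
| 0 | 0% | 0 to 21.8% |
| 1 | 6.7% | 0.2 to 31.9% |
| 2 | 13.3% | 1.7 to 40.5% |
| 3 | 20.0% | 4.3 to 48.1% |
| 5 | 33.3% | 11.8 to 61.6% |

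If three patients lost their only qualifying event, 5/15 would be reported as 2/15, or 3/15 as 0/15. The number three is an illustration, not a figure from the plan.

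**Assumed range.** Let s be the share of patients whose only qualifying event is of the exempted kind, and q the probability that it is filtered. The expected change in the rate is −s × q, and the chance of missing at least one of 15 patients is 1 − (1 − s × q)^15.
- s = 10%, q = 0.5: change −5 points; chance 1 − 0.95^15 = 53.7%.
- s = 10%, q = 1: change −10 points; chance 1 − 0.90^15 = 79.4%.
- s = 50%, q = 0.5: change −25 points.
- s = 50%, q = 1: change −50 points.
- q = 0, or s = 0 because exempted events would have been judged unrelated or occur only in patients already counted: change 0.

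Both s and q are assumptions; the documents give no value for either.

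**The case against.** The strongest reply is that the paragraph is coherent as written. It defines AEs broadly, narrows the definition, and then applies relatedness to what is left. An event judged an ordinary reaction to surgery has been attributed to the operation, so its cause is not indeterminable. Only such events are exempt, and a fever not judged ordinary must still be recorded. Counting every routine fever as indeterminable would load the device rate with the effects of surgery.

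Much of this stands. A reader might infer that the plan contradicts its own relatedness rule. The documents do not support that, because both sentences can be followed in sequence. A reader might also infer that the rate is biased low. That is not shown either: under-counting needs events to be wrongly exempted, and nothing in the documents says how often that would happen.

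It is also fair that some trace would remain. Section 2.5.2 lists vital signs, blood counts and antibiotic use among the data collected. The endpoint is secondary and descriptive, and neither fever nor constipation is in the MAE list of section 2.4.1. On seriousness, one may argue that the definition in endpoint (4) stands on its own and would capture a serious fever regardless.

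What the reply does not answer is the doubtful case. The text leaves it to unaided judgement, states no precedence, and keeps no list of what was exempted. Vital signs or an antibiotic entry may hint at an event but do not supply the missing relatedness assessment. The reading of endpoint (4) is plausible, but the plan does not state it.

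**Conclusion.** The concern holds as a risk with a known direction and an unknown size. An open-ended exemption, applied by judgement, acts before relatedness and seriousness are assessed. Wrong use of it can only lower the device-related AE rate at 6 and 12 months, and possibly the SAE rate.

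The only figure that follows from the plan itself is 6.7 percentage points for each patient whose sole qualifying event is dropped, with 15 patients in the denominator. The number of such patients may be zero. The larger shifts in the sizing rest on assumed inputs and show sensitivity, not expected bias. The primary endpoint is not affected. This is a cheap improvement, worth making because events left unrecorded cannot be reliably rebuilt at analysis.

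**What to change.** In section 2.4.2, endpoint (5), replace the recording exemption with a flag:

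- Record these events on the AE page with a tick-box: expected post-operative response (investigator judgement).
- Assess device relatedness and seriousness for every flagged event, so that the rule on indeterminable relation and the SAE definition apply to all of them.
- In section 3.2.4, report the device-related AE rate twice: including and excluding flagged events.

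The line excluding flagged events keeps the sponsor's present distinction, and the difference between the two lines shows how much depends on it. A closed list with objective criteria, plus a log of exempted events, would also narrow the gap. However, it would still leave the exempted events without a relatedness assessment unless the log required one.

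The cost is a short rewording in two sections, one tick-box, a few more AE entries in 15 patients, and possibly a higher rate on the inclusive line.
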